## **12. STATISTICAL CONSIDERATIONS**

### **12.1. General considerations**

This section describes the main analyses that will be carried out. The statistical analysis plan to be approved by the sponsor will include additional information on analyses, management of unavailable data and analytical methods. All data will be analysed with the SAS statistical analysis system. All analyses will be carried out mainly by descriptive statistical methods. Continuous endpoints will be described using mean and standard deviation, median, minimum, maximum, Q1 and Q3. Categorical endpoints will be described with frequencies and percentages as well as the exact 95% confidence interval of the relevant study variables. All results will be presented separately by treatment arm.

The final statistical analysis that will be the basis of the final report of the study will be done on the total population of 45 patients once the extension of the study has been completed. The data of the first 27 patients will be analysed in an intermediate statistical analysis.

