## **12.5. Analysis of secondary endpoints**

### **12.5.1. Efficacy assessments**

Efficacy analyses will be performed on the efficacy population defined above. For the evaluation of efficacy endpoints, the following analyses will be carried out separately for each dosage level:

- The evolution of the viral load from the baseline visit on days 3, 4, 7, 15 and 31 will be provided.
- The time to negative detection of COVID-19 by PCR will be calculated as the time that elapses in days from the date of randomisation to the first date of PCR with a negative result. The time to negative detection will be analysed following the Kaplan-Meier methodology, providing the median and the corresponding 95% confidence interval.
- The number and percentage of patients who die 7, 15 and 31 days after starting the treatment with plitidepsin shall be described.
- The number and percentage of patients who require mechanical ventilation and/or ICU admission at 7, 15 and 31 days will be provided.
- The number and proportion of patients requiring invasive mechanical ventilation shall be stated.
- The number and proportion of patients requiring non-invasive mechanical ventilation shall be stated.
- The number and proportion of patients requiring oxygen therapy shall be stated.

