4.6 Missing data

Missing data imputation is not foreseen.

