 - Moderate and Mild Patients following the FDA Classification
 - Moderate patients following the FDA Classification

b) COVID-19 evolution by PCR:

For the analysis of COVID-19 evolution by PCR, the number and percentage of patients who have taken the PCR test will be indicated at the baseline and at visit 4, 7, 15 and 31 describing the results (positive / negative) in those patients.

A list of PCR evolution of the patients from baseline to the last visit will be presented.

c) Time to negative detection of COVID-19 detection by PCR:

The time to negative detection of the detection of COVID-19 by PCR is defined as the time, in days, from the date of baseline PCR to the first PCR date with a negative result and does not have a positive result in the following PCR or having a negative result in the last PCR date (Day 31).

The following analyses will be presented.

The time to negative detection will be analyzed by the Kaplan-Meier method and the median and the 95% confidence interval will be provided.

- The number and percentage of patients with qualitative PCR at 4, 7, 15 and 31 days
- A descriptive table will be provided in which both variables are related to each of the variables indicated below:
 - Chronic lung disease (excluding asthma) (Yes; No).
 - Oxygen therapy on day 1 (Yes; No).
 - Plitidepsin dose
 - Days from symptoms until 1st dose of plitidepsin
 - Baseline severity of the disease
 - Age
 - Sex
 - Use of corticosteroids
 - Race
 - Use of other antivirals or other specific treatments for COVID 19

d) Deaths:

The number and percentage of patients who die within 7, 15 and 31 days after starting the treatment with plitidepsin will be described.

- From day 1 to day 7
- From day 8 to day 15
- From day 16 to day 31

In addition, cumulative table will be presented with the following groups:

- From day 1 to day 7
- From day 1 to day 15
- From day 1 to day 31

e) Oxygen therapy:

The number and percentage of patients requiring oxygen therapy on days 7, 15 y 31 after the start of plitidepsin treatment.

- From day 1 to day 7
- From day 8 to day 15
- From day 16 to day 31

In addition, cumulative table will be presented with the following groups:

- From day 1 to day 7
- From day 1 to day 15
- From day 1 to day 31

A descriptive table will be provided in which both variables are related to each of the variables indicated below at 4, 7, 15 and 31 days:

- Chronic lung disease (does not include asthma) (Yes; No).

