- Time to Hospital discharge (continuous): The time to Hospital discharge is defined as the time, in days, from the date of treatment start and the date of hospital discharge. In those patients who have not been discharged, the time, in days, from the date of first dose to the last available date will be calculated and it will be censored for time to event analyses. The description of the variable will be done separately depending on whether the patient has been discharged from hospital or not. The median and 95% confidence interval will be presented.
- Time from admission to Hospital discharge (continuous): The time to Hospital discharge is defined as the time, in days, from the date of admission and the date of hospital discharge
- Multivariate analysis will be done to evaluate the relationship of the main covariates in the analysis with Hospital discharge on Day 8 (Yes/No) and Hospital discharge on Day15 (Yes/No) by means of logistic regression models. More relevant exploratory covariates from the univariate analyses (p-value < 0.10) will be included in the multivariate analyses.
- Multivariate analysis will be done to evaluate the relationship of the main covariates in the analysis with time to hospital discharge by means of Cox proportional hazard models. More relevant exploratory covariates from the univariate analyses (p-value < 0.10) will be included in the multivariate analyses.
- Swimmer plot Hospital Discharge Day by Viral Load at Baseline, Disease Severity at Baseline and oxygen (yes/no) at baseline.

m) Class at discharge:

The time to hospital discharge (category 1) at 6-points ordinal scale will be analyzed by the Kaplan-Meier method and the median and the 95% confidence interval will be provided.

The analysis will be completed by the following subgroups:

- FDA classification
- Oxygen therapy on day 1
- Symptoms evolution less or equal/greater than 6 days.

The value of the 6-point ordinal scale will be derived from CRF data by using the following definition:

1. Discharge (Alive)
2. Hospital admission, not requiring supplemental oxygen.
3. Hospital admission, requiring supplemental oxygen.
4. Hospital admission, requiring high-flow nasal cannula or non-invasive mechanical ventilation.
5. Hospital admission, requiring extracorporeal membrane oxygenation or invasive mechanical ventilation.
6. Death.

In addition, the following analyses will be performed:

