Day 1 to Day 7				
Day 8 to Day 15				
Day 16 to Day 31				
Patients requiring non-invasive mechanical ventilation at, n (%)				
Day 1 to Day 7				
Day 8 to Day 15				
Day 16 to Day 31				
Patients requiring oxygen therapy at, n (%)				
Day 1 to Day 7				
Day 15				
Day 31				
Patients requiring oxygen therapy (high flow) at, n (%)				
Day 7				
Day 15				
Day 31				
Patients requiring oxygen therapy (low flow) at, n (%)				
Day 7				
Day 15				
Day 31				

This table will be also performed by age (<65 vs. ≥65 year old) (12.1.5.1)

This table will be also performed by FDA classification (12.1.5.2)

Table 12.1.6 Summary of Protocol-Specified Efficacy Endpoints 95%CI

Dose Cohort															
1.5 mg				2 mg				2.5 mg				Total			
N	%	Exact CI Lower	Exact CI Upper	N	%	Exact CI Lower	Exact CI Upper	N	%	Exact CI Lower	Exact CI Upper	N	%	Exact CI Lower	Exact CI Upper

(*) Patients requiring Invasive Mechanical Ventilation; Patients requiring Non Invasive Mechanical Ventilation; Patients requiring ICU.

This table will be also performed by age (<65 vs. >=65 year old (12.1.6.1)
This table will be also performed by FDA classification (12.1.6.2)

Table 12.1.7 Viral load change from baseline and negative detection

Mean change in viral load from baseline to, log10 copies/mL	Dose Cohort			
	1.5 mg N=X	2.0 mg N=X	2.5 mg N=X	Total N=X
Day 4				
Day 7				
Day 15				
Day 31				
Mean time from baseline until undetectable viral load (days)*				

All patients (12.1.7.1), Mild & moderate patients (12.1.7.2), moderate patients (12.1.7.3), severe patients (12.1.7.4).

(*) From baseline PCR

Table 12.1.8 Viral load at baseline and study outcome variables

	Viral Load at baseline			
	Low <4	Medium [4-7]	High >7	p-value(*)
Oxygen therapy				
Yes				
No				
Oxygen therapy Low flow				
Yes				
No				
Oxygen therapy High flow				
Yes				
No				
ICU admission				
Yes				
No				
NIMV				
Yes				
No				
IMV				
Yes				
No				
Death				
Yes				
No				
Days of hospitalization				
FDA Risk groups				
Mild				
Moderate				
Severe				

(*)Fisher's exact test for categorical variables. Kruskal-Wallis test for continuous variables.

Table 12.1.9 Patients with negative detection

Number of patients (%)	Dose Cohort			
	1.5 mg N=X	2.0 mg N=X	2.5 mg N=X	Total N=X
Day 4				
Day 7				
Day 15				
Day 31				

Table 12.1.10 Patients with negative detection according to initial viral load

Number of patients (%)	Dose Cohort			
	1.5 mg N=X	2.0 mg N=X	2.5 mg N=X	Total N=X
Low <4				
Medium [4-7]				

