High >7				
Total				

Table 12.1.11 Time to negative detection

Time to negative detection	Time to negative detection			p-value(**)
	N	Median	Range	
Viral load at baseline				
Low <4				
Medium [4-7]				
High >7				
Dose				
1.5 mg				
2.0 mg				
2.5 mg				
Age				
< 65 y.o.				
>=65 y.o.				
Sex				
Female				
Male				
Race				
White				
Other				
... (*)				

(*) FDA risk groups (Mild, moderate, severe), Oxygen need (Yes/No), Chronic lung disease (Yes/No), Corticosteroids (Yes/No), Other antiviral treatment for COVID-19 (Yes/No). Further variables could be added upon request

(**) Kruskal-Wallis

Table 12.1.12 Time to negative detection by corticosteroid duration

Time to negative detection	Corticosteroid duration		p-value*
	< 10 days	>= 10 days	
Dose			
1.5 mg			
2.0 mg			
2.5 mg			
Total			

(**) Kruskal-Wallis

Table 12.1.13 Oxygen therapy

Number of patients (%)	Dose Cohort							
	1.5 mg N=X		2.0 mg N=X		2.5 mg N=X		Total N=X	
	Oxygen therapy							
	Yes	No	Yes	No	Yes	No	Yes	No
Oxygen therapy at baseline								
Yes								
No								
Chronic Lung Disease								
Yes								
No								
Age								
< 65 y.o.								
>=65 y.o								
Gender								
Female								
Male								
Race								
White								
Other								
Viral load at baseline								
Low <4								
Medium [4-7]								
High >7								
FDA Risk groups								
Mild								
Moderate								
Severe								

Listing 12.1.14 Oxygen therapy evolution

Subject id	Dose	Visit	Date	Time	Oxygen therapy type	Flow

Table 12.1.15 Oxygen therapy onset day

Onset day	Dose Cohort							
	1.5 mg N=X		2.0 mg N=X		2.5 mg N=X		Total N=X	
From start of symptoms								
From first plitidepsin dose								
From corticosteroids use								

Table 12.1.16 Patients changing oxygen therapy

	Dose Cohort			
	1.5 mg N=X	2.0 mg N=X	2.5 mg N=X	Total N=X
From no Oxygen therapy to Oxygen therapy				
From low flow to high flow				
From high flow to low flow				

Table 12.1.17 Time in (ICU- Invasive M Ventilation – Non Invasive MV – in Hospital)

Time (days)	Dose Cohort			
	1.5 mg N=X	2.0 mg N=X	2.5 mg N=X	Total N=X
ICU				
Invasive mechanical ventilation				
Non Invasive mechanical ventilation				
Hospital*				

(*)From first infusion

Table 12.1.18 Reason for ICU discharge

Endpoint	Dose Cohort			
	1.5 mg N=X	2.0 mg N=X	2.5 mg N=X	Total N=X
Reason for ICU discharge, n (%)				
Taken back to the ward				
Death				

Table 12.1.19 ICU admission according to oxygen therapy or chronic lung disease

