	FDA risk groups at baseline			
	Mild	Moderate	Severe	p-value
Non-invasive mechanical ventilation, n (%)				
Yes				
No				
Invasive mechanical ventilation, n (%)				
Yes				
No				
High flow oxygen therapy, n (%)				
Yes				
No				
ICU admission, n (%)				
Yes				
No				
Days of hospital admission				
Days of symptom evolution				
CRP				
Ferritin				
AST				
ALT				
LDH				
Lymphocytes				

[figure not shown]
(*)It could be done by dose, if requested.

Figure 12.1.36 Plitidepsin: Viral load by Dose level (Median)

The lines represent the median value from baseline of the patients treated with viral load by central lab at the three dose levels in each time point(1.5mg n=x, 2.0 mg n=x, 2.5 mg n=x)

Figure 12.1.37 Plitidepsin: Viral load by Dose level (Mean)

The lines represent the mean value from baseline of the patients treated with viral load by central lab at the three dose levels in each time point (1.5mg n=x, 2.0 mg n=x, 2.5 mg n=x)

Figure 12.1.38 Plitidepsin: Viral load by FDA classification at baseline (Median)

[figure not shown]

Figure 12.1.39 Plitidepsin: Viral load by FDA classification at baseline (Mean)

[figure not shown]

Figure 12.1.40 Plitidepsin: Viral load by Oxygen support on day 1 (Median)

[figure not shown]

Figure 12.1.41 Plitidepsin: Viral load by Oxygen support on day 1 (Mean)

[figure not shown]
[figure not shown]
[figure not shown]

Figure 12.1.42 Time to negative detection of COVID-19 detection by PCR

[figure not shown]
(*) Table 12.1.37 will be also produced with median value and 95% confidence interval.

Figure 12.1.43 Time to Hospital discharge

[figure not shown]
(*) Table 12.1.38 will be also produced with median value and 95% confidence interval.

Figure 12.1.44 Time to Hospital discharge – All patients

[figure not shown]
(*) Table 12.1.39 will be also produced with median value and 95% confidence interval.

Figure 12.1.45 Time to Hospital discharge by FDA classification

(*) Table 12.1.40 will be also produced with median value and 95% confidence interval.

Figure 12.1.46 Time to Hospital discharge by time from symptoms (≤ 6 days vs >6 days)

(*) Table 12.1.41 will be also produced with median value and 95% confidence interval.

Figure 12.1.47 Swimmer Plot of Hospital Discharge Day by Viral Load at Baseline

[figure not shown]

Figure 12.1.48 Swimmer Plot of Hospital Discharge Day by Disease Severity at Baseline

[figure not shown]

Figure 12.1.49 Swimmer Plot of Oxygen therapy

[figure not shown]

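### Tables 12.1.7, 12.1.11 and 12.1.12 summarise time to negative detection by a mean or Kruskal-Wallis, with no rule for patients who never turn negative

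*SAP*

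**What the plan says.** **Planned method.** For time to negative PCR, Protocol 12.5.1 states: "The time to negative detection will be analysed following the Kaplan-Meier methodology". SAP 8.1 c) agrees: "The time to negative detection will be analyzed by the Kaplan-Meier method and the median and the 95% confidence interval will be provided". Figure 12.1.42 delivers this, and its note adds: "Table 12.1.37 will be also produced with median value and 95% confidence interval".

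**Other shells in SAP 12.1.**
- Table 12.1.11 reports time to negative detection by dose, baseline viral load, age, sex, race and other factors as N, median, range and a p-value footnoted "Kruskal-Wallis".
- Table 12.1.12 reports it by corticosteroid duration, with the same test.
- Table 12.1.7 has a row "Mean time from baseline until undetectable viral load (days"). This is the viral-load time of SAP 8.1 a), for which no method is named.

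**Incomplete times.** Protocol 12.1 says the SAP "will include additional information on analyses, management of unavailable data and analytical methods". SAP 4.6 states: "Missing data imputation is not foreseen". A censoring rule appears only for hospital discharge, in SAP 8.1 l), where time "from the date of first dose to the last available date will be calculated and it will be censored for time to event analyses".

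**The concern.** PCR and viral load are scheduled on days 4, 7, 15 and 31 after baseline (Protocol section 10), and the efficacy population generally needs only two weeks of follow-up (SAP 4.1). A patient can therefore be positive at day 31, or die or leave after day 15 still positive. Such a patient has no observed time to average or rank. With no imputation and no censoring rule, the literal reading is that Tables 12.1.7, 12.1.11 and 12.1.12 cover only patients who cleared.

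That conditions on the outcome. A dose that adds late clearers lengthens its own mean and median, while a dose that leaves the same patients positive drops them from the table. Two of these tables report by dose, and the dose is to be chosen on the study's joint safety and efficacy data (Protocol 6.1).

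A second problem is separate. Table 12.1.12 groups patients by how long they took corticosteroids, which is known only after baseline and may depend on when they cleared. The other-antiviral row of Table 12.1.11 is also post-baseline: COVID-19 antivirals are excluded at entry (Protocol 7.2, criterion 2), and other COVID-19 drugs are allowed only from 24 hours after the last dose (Protocol section 10, footnote 12). The corticosteroid row may be post-baseline too.

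**Working it through.** The plan states no figure to reproduce. All clearance rates below are assumptions; 15 per dose is from Protocol 6.1 and the visit days are from Protocol section 10.

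**1. Direction of the error.** Two arms of 15 have first negatives at days 4/7/15/31 of 2, 4, 4, 1 and 2, 4, 4, 4. The rest are still positive at day 31.

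| | Arm 1 | Arm 2 |
|---|---|---|
| Cleared | 11/15 | 14/15 |
| Negative by day 15 | 10/15 | 10/15 |
| Median, cleared only | 7 (6th of 11) | 15 (7th and 8th of 14) |
| Mean, cleared only | (8+28+60+31)/11 = 127/11 = 11.5 | (8+28+60+124)/14 = 220/14 = 15.7 |
| Kaplan-Meier share positive after days 4, 7, 15 | 13/15, 9/15, 5/15 | 13/15, 9/15, 5/15 |
| Kaplan-Meier median | day 15 | day 15 |
| Mean restricted to 31 days, all patients | (127 + 4×31)/15 = 16.7 | (220 + 1×31)/15 = 16.7 |

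The arm that clears more looks slower in a cleared-only table. Neither test is near significance (Kruskal-Wallis on the cleared p = 0.39, log-rank p = 0.46). What misleads here is the summary statistic.

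**2. Size of the shift in the mean.** Let q be the share still positive at day 31, with exponential clearance at rate −ln(q)/31 read at the four visits. The 31-day restricted mean is (1−q) × (cleared-only mean) + 31q.
- q = 5%: 13.0 cleared only, 13.9 for all.
- q = 20%: 16.4 and 19.3.
- q = 50%: 19.1 and 25.0.

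**3. Effect on p-values.** 5,000 simulated trials per row, three arms of 15. First negatives fall at days 4/7/15/31 in proportions 0.10/0.20/0.30/0.33, scaled to the stated total. Everyone else is censored at day 31. Entries are the share of trials with p < 0.05.

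| Cleared by day 31 | Kruskal-Wallis, cleared only | Kruskal-Wallis, never-negative ranked last | Log-rank |
|---|---|---|---|
| 93/93/93% | 4.9% | 4.5% | 5.0% |
| 95/90/85% | 5.0% | 6.1% | 7.7% |
| 93/93/80% | 5.2% | 9.3% | 12.7% |
| 93/77/60% | 4.4% | 27.2% | 36.6% |

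The first column stays near 5% by construction, because timing among the cleared was set equal. It shows that a cleared-only test cannot see doses that differ only in how many patients clear.

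**4. Deaths.** Naming Kaplan-Meier does not settle this. Take 15 patients: 2 negative at day 4, 3 at day 7, 2 deaths at day 10 without a negative, 4 negative at day 15, 3 at day 31, and 1 still positive.
- Deaths censored: 1 − (13/15)(10/13)(4/8)(1/4) = 0.917.
- Deaths kept as never negative: 12/15 = 0.80.

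**5. Corticosteroid duration.** 4,000 simulated trials of 45 patients, 93% cleared, no true steroid effect. Planned durations are 3/5/7/10/14 days with probabilities 0.20/0.20/0.10/0.25/0.25; groups are under 10 days and 10 days or more. If 0, 25 or 50% of those who clear stop steroids at their first negative, p < 0.05 occurs in 5, 9 or 19% of trials by log-rank and in 5, 10 or 24% by Kruskal-Wallis on the cleared. A log-rank test restricted to patients not negative by day 10 stays at 5–6%. Changing the test alone does not cure this problem.

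**The case against.** Several points on the other side stand.

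- **Kaplan-Meier is not abandoned.** A reader might infer that it was replaced. It was not: Figure 12.1.42 and its median table remain, and Kaplan-Meier implies right-censoring even where the text does not spell it out.
- **Not all three tables contradict the plan.** Table 12.1.7 reports a different endpoint with no named method, so its mean conflicts with no stated analysis. Tables 12.1.11 and 12.1.12 do not say which version they use.
- **Clearance is reported elsewhere.** A reader might infer that the number still positive can be seen nowhere. Table 12.1.9 counts negatives by dose at each visit, and Table 12.1.10 does so by baseline viral load. They would expose most of the example in step 1. They do not correct a mean, median or p-value, and SAP section 3 bases percentages on valid data, so missing samples could shrink the denominator.
- **Cleared-only is an inference.** The SAP never says such patients are dropped. Ranking them last would make Kruskal-Wallis workable with full follow-up to day 31, but that is not written either and would not rescue a mean.
- **The corticosteroid row is less certain.** The entry exclusion and 24-hour rule concern COVID-19 drugs, and SAP 9.6 lists high-dose corticosteroids under support treatment. These rules establish only the antiviral row as post-baseline. The duration grouping is post-baseline by its nature.
- **The analysis is descriptive** (SAP section 1), and no p-value decides anything.

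**Conclusion.** The point holds as a gap in the supporting tables and should be fixed. On the literal reading, Tables 12.1.7, 12.1.11 and 12.1.12 can rank doses or subgroups differently from the Kaplan-Meier output, and nothing says which governs. The post-baseline grouping in Table 12.1.12 is a second, independent fault.

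The size is unknown, because the documents do not give the share still positive. If nearly all patients clear, the difference is small: under a day in the mean at 5% still positive, and rejection rates of 4.5–7.7% in the first two simulated rows. It grows as doses differ in how many patients clear. The steroid figures rest on an assumed stopping habit that the documents do not describe.

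A reader might infer that dose selection would be reversed or that a false significant result is likely. The documents do not support that: the endpoint is secondary, dose choice rests on all safety and efficacy data, and no rule ties it to these tables.

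**What to change.** 1. In the shells of Tables 12.1.11 and 12.1.12, state whether the time is by PCR or by viral load.
2. In SAP 8.1 a) and 8.1 c), censor patients without a negative at their last test. State how deaths without a negative are handled, for example kept as never negative through day 31.
3. In Tables 12.1.7 and 12.1.11, replace the mean and the cleared-only median with number negative, number censored and the Kaplan-Meier median with 95% confidence interval. For dose and baseline factors, replace Kruskal-Wallis with log-rank, or drop the p-values. Dropping them suits a descriptive plan with 45 patients.
4. In Table 12.1.12, and in the treatment rows of Table 12.1.11 where treatment starts after baseline, drop the p-value or use a landmark analysis.
5. State that the Kaplan-Meier result is the reference.

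The cost is SAP wording and reprogramming of a few tables. No new visits, samples or data are needed.
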